The study will use a variety of techniques to identify genetic characteristics associated with the specific CHDs of interest. Microarray analysis will be implemented to detect single nucleotide polymorphisms (SNPs) and copy number variants (CNVs). Genome wide association studies (GWAS) and evaluation of CNVs will seek to identify genetic variants associated with major categories of CHD (e.g., conotruncal defects, left-sided obstructive lesions) and, as numbers allow, within potentially more homogenous subsets (e.g., tetralogy of Fallot, hypoplastic left heart syndrome).

Whole exome sequencing will generate sequence data for all protein coding regions and whole genome sequencing will generate sequence data for the entire genome. Targeted analysis using molecular inversion probe sequencing (MIPS) complements these approaches by providing assessment of select genomic regions. Compared to publically available sequence data, rare variants with potential association to disease will be identified. Based upon data from GWAS, CNV analysis, whole exome sequencing, and whole genome sequencing, candidate genes or loci will be identified. Using capture based techniques and high throughput sequencing, sub genomic libraries consisting of these candidates will be resequenced in large numbers of patients. Such an effort will provide data that supports or refutes their causality in CHD and will define the spectrum of mutation type and location associated with CHD.

New genetic tools are developed frequently, so other genetic techniques that become available during the study period will be evaluated and used as appropriate to achieve the study aims.

To identify genetic variants that are associated with a specific CHD or clinical outcome, several analytic approaches will be undertaken. Two examples include a familial approach using case-parent triad design and a case-control approach. The case-parent triad design will identify maternal genetic effects and de novo changes by comparing analyses of the proband's DNA with that of the proband's parents. In the case-control design, frequencies of identified genetic variants will be compared between cases and controls. As the technology and science advance, newer analytic approaches are likely to be added.

C.4 Return of Genetic Testing Results

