If a subject should wish to withdraw from the study, data and samples collected prior to the withdrawal will remain in the database and biorepository, respectively. The subject might wish to have all research being conducted on his/her sample stopped. These requests will result in the sample being destroyed, the subject's name removed from the site-maintained enrollment log, and all data de-identified in the database. Clinical and genetic data already obtained would remain in the databases. If a subject wishes to have all research being conducted on their samples stopped and their samples destroyed, the participant will be asked to provide this request in writing to the site Investigator.

Data from participants who are unable to give the requested volume of blood will be kept in the study database. All data collected will remain in the database, except as noted above.

E.7 Early Termination of a Subject's Participation

The study PI may choose to terminate a subject's participation if it is felt to be in his/her best interest for clinical or other reasons.

E.8 Study Termination

The study may be terminated only by the Sponsor or other related oversight organizations.

F. Statistical and Analytical Approaches

Various state-of-the-art technologies will be used to generate data on genetic variation that may be related to CHDs. As the technologies and methods for assessing genetic variation are rapidly evolving, it is likely that the most appropriate statistical approaches for analyzing the data will also change with time. However, examples of current approaches are discussed below.

Public databases will be used to provide information on pediatric and population controls. Depending on the available data and the specific hypothesis being evaluated, statistical analyses will be based on data from either case-parent triads or cases and controls.

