Sample size and Power: Given the potentially large number of statistical tests that will be performed to assess SVs, it will be necessary to set the p-value for declaring statistical significance quite low. However, unlike GWAS studies, the number of tests to be performed cannot be specified *a priori*. For illustrative purposes, sample size requirements are presented for a p-value threshold of 5×10^{-5} (accounting for 1,000 comparisons). However, this threshold will be reconsidered when SV data are available, and can be used to estimate the number of comparisons that will actually be made. Minimum sample size requirements to achieve adequate power (>80%) to detect genotype relative risks ranging from 1.2-2.0 for common variants (minor allele frequency (MAF)≥0.10) and, from 1.2-5.0 for rare variants (MAF=0.001 and 0.01), under an additive model of inheritance, assuming a 1:4 case-control ratio are provided in Table 2. These estimates were obtained using the computer program Quanto (version 1.2.3, Gauderman and Morrison, http://hydra/usc.edu/gxe).

Table 2: Minimum sample size requirements	for SV analyses using
---	-----------------------

 $p < 5x10^{-5}$ as the threshold for significance.

Genotype Relative Risk	Frequency of High Risk Allele						
	0.001	0.01	0.10	0.20	0.30	0.40	0.50
1.2	404,600	40,900	4,600	2,600	2,100	1,800	1,800
1.4	108,200	11,000	1,200	740	590	540	540
1.6	51,200	5,200	610	370	280	280	280
1.8	30,500	3,100	310	230	190	180	180
2.0	20,600	2,100	355	160	130	130	130
3.0	6,400	660				1	
4.0	3,400	350					
5.0	2,200	230					

F.3 Candidate Gene, Whole-Exome, And Whole-Genome Sequence Analyses

Evaluation of sequence variants will be based upon comparison with publically available sequence data. In general, these analyses will focus on identification of rare variants and, in particular, variants that are identified in as few as one case and are unobserved among a large number of control sequences. Power calculations are not provided for the proposed sequence analyses, since the identification of rare variants found only in cases is of interest regardless of the associated p-value.

F.3.1 Analysis and annotation of the exome or MIPS sequencing data

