We will use a mix of publicly available and privately developed tools. First, we will map sequence reads to the reference human genome. Reads outside of the targeted sequences will be discarded and statistics on coverage will be collected from the remaining reads. Once the likely mapping locations are identified, the reads will be aligned allowing gaps to the reference genome using BWAmem and comparable software packages in order to identify indels. Potential variants will be called using TERRA, Genome Analysis Toolkit or similar platforms, as well as custom tools already developed in-house at several of the participating centers. We will identify known variants from dbSNP, publicly available genomes and exomes, including the 1000 Genomes Project, TOPMed, UK Biobank, and the Genome Aggregation Database, and exomes previously sequenced at the participating centers.

Sequence variants will be filtered for quality, using criteria such as [30]:

- a. Calls with a Phred-like quality score of less than 45 will be excluded
- b. Reads supporting the major and minors alleles should have different start and end points
- c. Total reads at variant bases should be > 10

For remaining sequence variants lying within exons, their predicted effect on the encoded protein will be determined and deleterious effects predicted, e.g., with Polyphen or predicted premature termination of the protein. The degree of evolutionary conservation will be assessed for nonsynonymous changes using phyloP or similar scores calculated from multiple alignments of >40 vertebrate species, which are available from the University of California Santa Cruz genome browser (http://genome.ucsc.edu) as well as comparison with invertebrate orthologues.

Rare exonic variants that alter conserved residues and are predicted to have significant impact on protein function in genes will be studied further, such as those in genes that are expressed during

development and/or in cardiac tissues. Variants per gene, or per gene class, will be compared with overall or ethnically matched control samples to determine any association with CHD. When appropriate, segregation analyses within the family will be assessed and Lod scores determined. In addition, sequence analyses of that gene in unrelated affected samples will be performed, and newly discovered variants will be examined as above. The significance of rare variants found only in affected cases will be assessed by p-values.

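### F.3 selects variants because controls lack them and F.3.1 gives variants found only in cases a p-value; a frequency test against those same controls would not be valid

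*Protocol*

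**What the plan says.** **Selection.** C.3 speaks only of rarity: "Compared to publically available sequence data, rare variants with potential association to disease will be identified". F.3 repeats the basis ("Evaluation of sequence variants will be based upon comparison with publically available sequence data") and goes further, placing particular focus on "variants that are identified in as few as one case and are unobserved among a large number of control sequences". F.3.1 says how known variants are recognised: "We will identify known variants from dbSNP, publicly available genomes and exomes", together with exomes sequenced earlier at the centers.

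**Controls.** Section F states: "Public databases will be used to provide information on pediatric and population controls".

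**Testing.** C.3 describes the case-control approach in general terms: "In the case-control design, frequencies of identified genetic variants will be compared between cases and controls". F.3.1 compares variants per gene or gene class with overall or ethnically matched control samples to look for association. It ends that account with: "The significance of rare variants found only in affected cases will be assessed by p-values".

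**Conflict.** F.3 gives no power calculation for the sequence analyses, on the ground that case-only rare variants matter whatever their p-value. F.3.1 nevertheless assesses their significance by p-values.

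**The concern.** A test that compares frequencies in cases and controls assumes that the control count was free to vary. If a variant enters the analysis because no control carries it, that count is fixed at zero before the test is run. The p-value then measures how many harmless rare variants the cases happened to carry. Pooling variants per gene does not cure this, and neither does perfect variant calling.

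Nothing in the protocol keeps the filtering data apart from the test controls, or requires the same filter in both groups. Gene discovery is the primary aim. Genes that carry many harmless rare variants would be favoured and could move on to resequencing in further patients and to iPSC work.

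**Working it through.** The protocol gives no sample size, power or significance threshold for the sequence analyses, so there is no figure to reproduce. The nearest threshold, for structural variants in F.2, does reproduce: 0.05 / 1,000 = 5×10⁻⁵.

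**Calculation 1: Fisher test with the control count fixed at zero**

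Assumptions:
- 2,000 cases and 8,000 controls. The 1:4 ratio is stated only for the structural-variant table and is borrowed here.
- 20,000 genes without effect, and a threshold of 0.05 / 20,000 = 2.5×10⁻⁶.
- Each qualifying variant is seen once in the pooled data.

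With k case carriers and no control carriers, the one-sided p is C(2000,k) / C(10000,k), or about 0.2^k:

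| k | p |
|---|---|
| 2 | 0.040 |
| 6 | 6.4×10⁻⁵ |
| 8 | 2.53×10⁻⁶ |
| 9 | 5.0×10⁻⁷ |

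So k ≥ 9 passes 2.5×10⁻⁶, and k ≥ 2 passes 0.05. Let the number of case-only variants in a null gene be Poisson with mean m. Expected false genes are then 20,000 × P(K ≥ 9), and the share significant at 0.05 is P(K ≥ 2) = 1 − (1 + m)e^(−m). In the comparison columns, control-only variants are counted too, as Poisson with mean 4m.

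| m | False genes, control count forced to 0 | False genes, control-only counted | p<0.05, forced to 0 | p<0.05, counted |
|---|---|---|---|---|
| 1 | 0.02 | 0.0006 | 26% | 1.9% |
| 1.5 | 0.55 | 0.003 | 44% | 2.0% |
| 2 | 4.7 | 0.007 | 59% | 2.2% |
| 4 | 427 | 0.021 | 91% | 3.0% |
| 6 | 3,055 | 0.023 | 98% | 3.3% |

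**Calculation 2: simulation of genes without effect**

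Assumptions: 2,000 genes per scenario; 1,000 or 3,000 cases; controls 1:1 or 1:4; 100 or 500 rare sites per gene; carrier frequency per site gamma (shape 0.1, scale 0.0005) capped at 0.001; a reference set the same size as the control set; two-sided Fisher test. This gives eight scenarios. Ranges below run across them.

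| Rule | p<0.05 | p<5×10⁻⁵ |
|---|---|---|
| No filter | 1.8% to 5.1% | none |
| Same set filters and tests, 100 sites | 14.4% to 48.5% | 0% to 0.7% |
| Same set filters and tests, 500 sites | 99.3% to 100% | 54.2% to 98.2% |
| Separate filter set, but list built from variants seen in cases | 4.0% to 92.0% | up to 15.3% |
| Separate filter set, same rule in both groups | 1.3% to 4.3% | none |

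The fourth row matters for the remedy: a separate database is not enough if the variant list still comes from the cases. The last row shows that the problem goes away once the filter set is separate and the rule is the same in both groups.

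**The case against.** The strongest reply is that the faulty procedure is permitted rather than prescribed, and much of that stands.

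- A reader might infer that one public dataset both filters and tests. No section says so. The filtering sources in F.3.1 and the control samples for the gene comparison are described in different words, and for whole-genome data F.3.1 processes control samples jointly with PCGC samples.
- A reader might infer that control-only variants go uncounted in the per-gene comparison. The text does not say that. The ordinary reading is a count in both groups, and the filters stated just before it are rarity, conservation and predicted impact.
- C.3 says rare, not absent. Its statement that "frequencies of identified genetic variants will be compared between cases and controls" describes the case-control design generally and is not tied to the filtered variants.
- The p-value sentence names no test, threshold or comparator, and no section declares a gene associated on that p-value alone.
- Section F presents its methods as current examples that are likely to change, and a statistical analysis plan may name databases and counting rules.

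What does not fall is the pairing of F.3 with F.3.1. Being found only in cases already means a control count of zero, and the protocol itself attaches a p-value to that class. This is a stated rule, not a detail left for later. Resequencing is no safeguard as written: C.3 does it in patients, and F.3.1 examines newly found variants in the same way.

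**Conclusion.** The point holds for p-values on variants selected for absence from controls, where the p-value is a frequency test against those controls. Such a p-value is not valid, and F.3 and F.3.1 disagree on whether it matters.

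The size cannot be read from the protocol. Under the assumptions of Calculation 1 it runs from negligible at the strict threshold (0.02 false genes at a mean of 1) to severe (427 at a mean of 4). The mean per gene is assumed, and the restriction to conserved, high-impact variants would lower it. At nominal 0.05 the inflation is already 26% at a mean of 1, but the protocol sets no such threshold for these analyses. If the filter set and the test controls overlap only in part, inflation lies between the simulated extremes. A frequency cut-off above zero would also reduce it.

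The documents do not support a claim that hundreds of false genes will be reported, or that every sequence comparison is affected. De novo, case-parent triad and segregation or Lod analyses do not rest on this contrast.

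**What to change.** In F.3 and F.3.1:

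1. Define qualifying variants by a rule applied identically to cases and controls: a frequency cut-off either in a reference set separate from the test controls, or in cases and controls pooled.
2. Count every qualifying variant in both groups, including those seen only in controls. Do not build the list from variants seen in cases.
3. Report variants selected for absence from the comparison controls descriptively, without an association p-value from those controls.
4. Reconcile F.3 with F.3.1 on the role of p-values for case-only variants.

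The cost is protocol wording and a changed filtering and counting step, with no new participants or samples. The one real downside is that a database used for filtering cannot also be the control set for the same test, unless pooled filtering is chosen.

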Participants with CHD or subjects with normal heart structure and function who have a genotype strongly associated with CHD (such as Trisomy or Chr22q deletion) will be recruited from prenatal and pediatric centers, pediatric cardiology and adult congenital heart centers. Patients with genetic syndromes such as Trisomy or Chr22q deletion will have been diagnosed and well categorized. Participants with isolated prematurity-associated patent ductus arteriosus, isolated patent foramen ovale or isolated pulmonary stenosis secondary to twin-twin transfusion syndrome will be excluded from the study. Family members will be recruited whether or not they have a CHD history. There will be no restrictions to participation based on age, sex or ethnicity. Existing published and preliminary data [28, 29] suggests there will be a slight preponderance of male to female candidates for the study. Whenever possible, the study will recruit 'trios' of participants--children, mothers and fathers- as well as extended family members when appropriate and feasible.

For the iPSC component of the study, all CHD participants will be presented with the option to participate as part of the overall consenting process. Eligibility for this optional part of the study will

occur after enrollment and participation in the main study has begun. Those main study participants who meet the requirements for this optional part of the study and agreed to participation during the consenting process will be asked to provide the additional blood sample as described in the consent form. We will contact currently enrolled affected subjects or subjects with a genotype strongly associated with CHD or parent of affected subjects who have a defined gene mutation and are either still active subjects or are subjects who have given permission for future contact.

Recruitment strategies will include publicizing the study on the Bench to Bassinet website and individual site websites, through brochures and other printed materials, formal presentations by study investigators to their divisions or departments, individual conversations between investigators and patients, and other standard recruitment tools.

C.3 Genetic and Genomic Analyses

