- 1. A sample of whole blood will be obtained from the proband from an indwelling line or in conjunction with a clinically warranted venipuncture whenever possible. Otherwise, trained technicians will perform phlebotomy to obtain a sample of blood from the willing child/family. A sample will be acquired only if drawing said sample will not in any way harm the participant's clinical status or precipitate the need for a blood transfusion. The blood sample will be used to extract DNA and may be used to make a cell pellet and/or immortalized lymphoblastoid cell line to allow for a renewable resource. Approximately 3-10 ml of blood will be drawn from an infant while 10-15 ml will be drawn from anyone older than one year (the volume will not exceed that permitted by weight and will not exacerbate any existing medical conditions). While blood is preferred and should be prioritized, if blood cannot be drawn or the enrollee is unwilling, then a saliva sample (age permitting) will be obtained. In the event that the proband dies following consent, an autopsy specimen may be obtained. We may also request permission to use blood samples collected for clinical procedures that would otherwise be discarded.
- 2. We will ask permission to use leftover/discarded samples taken during medically indicated procedures for an enrolled proband participant or a mother who is pregnant with an in-utero diagnosed proband participant during pregnancy including, but not limited to, leftover/ discarded DNA from amniocentesis, chorionic villus samples, or percutaneous umbilical blood sampling. Participation in this collection of discarded samples is optional for all sites. All sites will follow

their institutional procedures and guidelines as outlined in IRB reliance and submission documents.

- 3. If the proband participant is undergoing a medically indicated surgical procedure, then tissue that during the course of surgery would have been discarded (such as discarded atrial tissue resulting from cannulation for cardiopulmonary bypass) may be acquired for research purposes. No additional sample will be collected specifically for this purpose. Participation in this collection of discarded samples is optional for all sites. All sites will follow their institutional procedures and guidelines as outlined in IRB reliance and submission documents.

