- OPTIONAL blood sample for iPSC Subjects with a defined gene mutation (identified from their initial enrollment in the study) will be identified and will be recontacted by the study site. If the subject consents, an additional blood sample (3-5ml) will be obtained and used for generating iPSCs.

D.1.2 Family samples

- 1. Up to 15 ml of whole blood will be drawn from consenting immediate and/or extended family. Blood draws will be done on site or a packet containing instructions for off-site phlebotomy will be sent. If a grandparent, sibling, or distant relative is unwilling or unable to undergo a venipuncture, then a sample of saliva will be acquired. In some instances, samples will be collected by mail. In this event, we will provide a self-addressed stamped return kit for the sputum or blood sample which will be in full compliance with standards for shipping biological materials.
- 2. We will ask permission to use leftover/discarded samples taken during medically indicated procedures during pregnancy including, but not limited to, leftover/ discarded DNA from amniocentesis, chorionic villus samples, or percutaneous umbilical blood sampling from prenatal cases. Participation in this collection of discarded samples is optional for all sites. All sites will follow their institutional procedures and guidelines as outlined in IRB reliance and submission documents.
- 3. If an affected relative is undergoing a surgical procedure, then tissue that during the course of surgery would have been discarded (such as discarded atrial tissue resulting from cannulation for cardiopulmonary bypass) may be acquired for

research purposes. No additional sample will be collected specifically for this purpose. Participation in this collection of discarded samples is optional for all sites. All sites will follow their institutional procedures and guidelines as outlined in IRB reliance and submission documents.

D.2 Clinical and Phenotypic Data

Clinical and phenotypic data will be collected as outlined in detail below. In addition, participants will be asked to agree to future contact for the purposes of obtaining additional information. Medical record review and/or programmatic extraction of structured data from the medical record may occur at baseline and longitudinally during the study period for patients who have not been withdrawn.

D.2.1 Proband participant clinical data collection

Proband participant data will include:

- 1. Cardiac anatomy

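### The family blood-draw rule in D.1.2 allows up to 15 ml at any age and omits the infant range and the weight and clinical-status conditions that D.1.1 sets for probands

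*Protocol*

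**What the plan says.** Protocol D.1.1 (Proband participant samples), item 1, sets the proband's volume by age: "Approximately 3-10 ml of blood will be drawn from an infant while 10-15 ml will be drawn from anyone older than one year". It adds a limit in parentheses: "the volume will not exceed that permitted by weight and will not exacerbate any existing medical conditions". It also makes the draw conditional: "A sample will be acquired only if drawing said sample will not in any way harm the participant's clinical status". The same sentence rules out a draw that would bring on a need for transfusion.

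Protocol D.1.2 (Family samples), item 1, states its own volume: "Up to 15 ml of whole blood will be drawn from consenting immediate and/or extended family". The draw may be done on site, or "a packet containing instructions for off-site phlebotomy will be sent". The alternative to blood is saliva: "If a grandparent, sibling, or distant relative is unwilling or unable to undergo a venipuncture, then a sample of saliva will be acquired". Item 1 contains no age band, weight limit or clinical-status condition, and does not point back to D.1.1.

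On who can be a relative, C.2 says "Family members will be recruited whether or not they have a CHD history" and "There will be no restrictions to participation based on age, sex or ethnicity". E.4 provides for consent by a parent or guardian on behalf of a minor.

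**The concern.** The protocol recognises in D.1.1 that a small or sick child needs a smaller volume and a check on clinical status before blood is taken. D.1.2 covers people who can be just as small and just as sick, yet carries none of that over. Two infants of the same age and weight in one family would then be under different written limits, depending only on which of them is enrolled as the proband.

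Participant protection is at stake in a multi-center study that enrols families. Sites and off-site phlebotomists will work from the written volume, and for a relative the only written limit is 15 ml. No aim, power figure or analysis is affected.

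**Working it through.** The check is a comparison of passages with one ratio.

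**1. The two rules side by side**

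| Element | D.1.1, proband | D.1.2 item 1, family |
|---|---|---|
| Infant volume | about 3-10 ml | up to 15 ml (no infant band) |
| Older than one year | 10-15 ml | up to 15 ml |
| Weight limit | yes | not stated |
| Existing medical conditions | yes | not stated |
| Clinical status and transfusion | yes | not stated |
| Off-site phlebotomy | not mentioned | allowed |
| Reference to the other section | none | none |

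Above one year of age the two upper figures agree at 15 ml, and only the conditions differ. For infants both the volume and the conditions differ.

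**2. Can an infant fall under D.1.2?** Yes, by four steps.
- D.1.2 item 1 names siblings among those who may be asked for venipuncture.
- C.2 places no age restriction on participation and recruits relatives with or without CHD.
- E.4 lets a parent or guardian consent for a minor, so the word consenting in D.1.2 does not restrict it to adults.
- D.1.2 item 3 refers to affected relatives having surgery. That item concerns discarded tissue, not blood, but it shows that a relative with a heart defect may be handled as family.

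**3. Does another section close the gap?** None found.
- I.1.2 (Blood draw) lists discomfort, bruising, slight bleeding and infection, and gives no volume, age or weight limit.
- Deference to institutional procedures appears in D.1.2 items 2 and 3, on leftover samples and discarded tissue, but not in item 1.
- The saliva alternative in D.1.2 depends on a relative being unwilling or unable. It is not tied to weight or clinical status.

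**4. Size.** Family ceiling divided by the top of the infant-proband range: 15 ml / 10 ml = 1.5.

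The documents give no body weights. For illustration only, volume divided by assumed weight gives:

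| Assumed weight | 15 ml | 10 ml |
|---|---|---|
| 3 kg | 15/3 = 5.0 ml/kg | 10/3 = 3.3 ml/kg |
| 5 kg | 15/5 = 3.0 ml/kg | 10/5 = 2.0 ml/kg |
| 10 kg | 15/10 = 1.5 ml/kg | 10/10 = 1.0 ml/kg |

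The ratio of 1.5 is the same at every weight. The 10 ml column takes no account of D.1.1's weight limit, which could lower the proband's volume further.

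**The case against.** Four points can fairly be made for the protocol.

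**The family figure is a ceiling.** A draw of 3-10 ml from an infant sibling satisfies both sections. This stands, so it would be wrong to say that the sections strictly contradict each other. D.1.2 is silent where D.1.1 speaks, and its ceiling permits what D.1.1 would not.

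**D.1.1 may have been meant more widely.** Its item 1 speaks of the participant, the enrollee and anyone older than one year, whereas items 2 and 3 of the same section specify the proband participant. The wider reading is arguable. But the section is headed for probands, and D.1.2 then states a separate volume without citing it. If the wider reach was intended, a cross-reference would say so.

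**Practice may supply the limits.** Sites may apply their own rules, I.2 commits the study to good clinical practice, and the off-site instructions, which are not in the document, may carry age or weight limits. This may be so, but the protocol did not leave the matter to practice for probands.

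**Infant relatives may be few.** The protocol does not give their number. This limits the reach of the point, not its correctness.

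A reader might also infer two stronger things that the protocol does not support. One is that the minimal-risk statement in I.4 is false for infant relatives. I.4 rests on the absence of therapeutic interventions, and the protocol gives no volume threshold against which to test it. The other is that nobody can exercise judgement at an off-site draw. The text shows only that D.1.2 attaches no conditions to it.

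**Conclusion.** The point holds as an inconsistency between D.1.1 and D.1.2. Followed as written, D.1.2 permits up to 15 ml from an infant relative, 1.5 times the top of the range for an infant proband, with none of the weight, existing-condition, clinical-status or transfusion conditions stated for the proband, whether on site or off site.

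This rests on reading D.1.1 as its heading indicates, as a rule for probands, and on infant relatives being eligible, which C.2, D.1.2 and E.4 together support. The ratio needs no outside assumption; the per-kilogram figures depend on assumed weights and are only illustrative. It should be corrected because it concerns the protection of small children, but it leaves the study's design and analyses unchanged.

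**What to change.** Reconcile D.1.1 and D.1.2 for infant and child relatives, for example by stating in D.1.2 whether D.1.1's limits and conditions also apply to family draws. Align the off-site phlebotomy instructions with the reconciled text, and the consent text where it states a volume. The sponsor and the single IRB decide the volumes and conditions; this review proposes none.

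The cost is a short text edit. If the reconciled text lowers the volume for infant relatives, a few of them may yield less DNA. Saliva should not be assumed to make up the difference at that age, since D.1.1 makes it conditional on age.
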